### 6.2.1 Hematologic Toxicities

**Table 6. Hematologic toxicity dose reductions for 5-AZA**

Grade	ANC a	Platelets	Hemoglobin	Action
1	<LLN to 1,500/ $\mu$ L	<LLN to 75,000/ $\mu$ L	< LLN to 10 g/dL	None
2	1000-1499/ $\mu$ L	50,000 to 74,999/ $\mu$ L	8 – 10 g/dL	None
3	500-999/ $\mu$ L	25,000 to 49,999/ $\mu$ L	< 8 g/dL	
-1st Occurrence: Hold current dose until ANC <math>\geq</math> 1,000/<math>\mu</math>L, platelets <math>\geq</math> 50,000/<math>\mu</math>L, and hemoglobin <math>\geq</math> 8 g/dL. Do not replace missed doses. Restart next treatment at 30 mg/m^2 dose.
 
-2nd Occurrence: Discontinue protocol therapy.
 
-If therapy held > 3 weeks: Discontinue protocol therapy.

4	<500/ $\mu$ L	<25,000/ $\mu$ L	Life-threatening consequences; urgent intervention indicated	
-1st Occurrence: Hold current dose until ANC <math>\geq</math> 1,000/<math>\mu</math>L, platelets <math>\geq</math> 50,000/<math>\mu</math>L, and hemoglobin <math>\geq</math> 8 g/dL. Do not replace missed doses. Restart next treatment at 30 mg/m^2 dose.
 
-2nd Occurrence: Discontinue protocol therapy.
 
-If therapy held > 3 weeks: Discontinue protocol therapy.

aNote: G-CSF (Filgrastim) 5 mcg/kg/day may be added for low ANC on day of treatment BEFORE a dose reduction is instituted at treating physician's discretion. This will be continued until anticipated nadir has passed and ANC <math>\geq</math> 1000. Neulasta® is NOT allowed.
				

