### 6.2.2 Non-hematologic toxicities

5-AZA will be continued at the original dose if the adverse event is grade 0-2. For grade 3-4 toxicities related to study drug, 5-AZA will be held until improvement of symptoms to grade 2 or below. After the first episode, the dose will be reduced by 25%. After the second episode, the protocol therapy will be discontinued. The investigator will determine whether the toxicity is related to study drug. The investigator may prescribe any concomitant medications as necessary, except for other anti-cancer therapy, for the management of adverse effects.

ATRA will be continued at the original dose if the adverse event is grade 0-2. For grade 3-4 toxicities related to study drug, ATRA will be held until improvement of symptoms to grade 2 or below. After the first episode,

the dose will be reduced by 25%. After the second episode, the protocol therapy will be discontinued. The investigator will determine whether the toxicity is related to study drug. The investigator may prescribe any concomitant medications as necessary, except for other anti-cancer therapy, for the management of adverse effects.

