**Table 7. Non-hematologic toxicity dose reductions for 5-AZA and ATRA**

NCI CTC Grade	5-AZA	ATRA
0-2	No change from original starting dose	No change from original starting dose
3 -4	Hold until resolved to $\leq$ Grade 2, then reduce to 30 mg/m^2	Hold until resolved to $\leq$ Grade 2, then reduce to 34 mg/m^2
Second episode of grade 3 or 4 toxicity	Remove subject from trial	Remove subject from trial

The administration of 5-AZA will be reported in a log book by the clinical trial staff. All patients will receive a study medication diary to log medication administration and adverse events for both 5-AZA and ATRA (See Appendix A).

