## **8. STATISTICAL CONSIDERATIONS**

### **8.1 Study Design/Study Endpoints**

The primary endpoints will be the disease progression-free rate at the end of the treatment phase 1 and safety of the combination of 5-AZA and ATRA. Disease progression is defined by composite of PSA or radiographic progression relative to period baseline (start of treatment phase 1), whichever occurs first. PSA levels will be measured on day 1 of each cycle. For assessment of PSA progression, see section 3.2.1 above. CT A/P and bone scan will be performed every 3 cycles. For assessment of radiographic progression, see section 3.2.2 above. Safety will be assessed by the recording of adverse events, monitoring of vital signs and physical examinations, safety laboratory evaluations, and 12-lead ECG. Adverse events will be graded per the Common Terminology Criteria for Adverse Events (CTCAE) version 4.0. Therapy will be continued at the original dose if the adverse event is grade 0-2. For grade 3-4 toxicities, therapy will be held until improvement of symptoms to grade 2 or below. The dose will then be reduced by 25% of original for each episode. A maximum of 2 dosage reductions will be allowed. The third occurrence will result in removal of the patient from the study.

The secondary endpoints will be time to tumor progression from start of treatment phase 1 and the measurement of dormancy biomarker levels in relation to disease states: tumor progression and disease progression. To determine the relation between dormancy biomarkers and disease states, every 3 cycles, we will measure the dormancy biomarkers, TGF $\beta$ 2, BMP7, BMP4, GAS6, retinoic acid, NR2F1, in BM aspirates and peripheral blood.

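### For a first grade 3-4 hematologic event, the rule for ATRA has conflicting scope: Table 6 is silent on it, while section 8.1 holds and reduces therapy without a hematologic exception

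*Combined protocol and SAP*

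**What the plan says.** Table 6 in section 6.2.1 is headed "Hematologic toxicity dose reductions for 5-AZA". For a first grade 3 or 4 event it calls for a hold until counts recover and then says: "Restart next treatment at 30 mg/m 2 dose". That figure is a 5-AZA dose. No ATRA dose or ATRA instruction appears in the table. For long interruptions it says: "If therapy held > 3 weeks: Discontinue protocol therapy".

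Table 7 is headed "Non-hematologic toxicity dose reductions for 5-AZA and ATRA" and has a separate ATRA column. The ATRA text that goes with it is in section 6.2.2, on non-hematologic toxicity: "For grade 3-4 toxicities related to study drug, ATRA will be held until improvement of symptoms to grade 2 or below".

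Section 8.1 names as a primary endpoint the "safety of the combination of 5-AZA and ATRA". The same paragraph then gives its own rule: "For grade 3-4 toxicities, therapy will be held until improvement of symptoms to grade 2 or below". It continues: "The dose will then be reduced by 25% of original for each episode". Neither sentence names a drug, and neither sets hematologic events apart.

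**The concern.** A patient with a first grade 3-4 cytopenia falls under Table 6 and, by its wording, under section 8.1 as well. Staff working from section 6 find nothing to do about ATRA. Staff working from section 8.1 can reasonably hold and reduce both drugs. The regimen given afterwards could then depend on which section was consulted.

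Safety of the combination is a co-primary objective (section 2.1). Section 3.1 schedules both randomized groups to receive the drugs, in phase 1 or phase 2, so the question can arise for any of the 20 planned evaluable patients. If ATRA dosing after a cytopenia varies with the reader, the safety summary describes a mixture of regimens that the plan did not intend.

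**Working it through.** **Inputs**
- Starting doses and days: 5-AZA 40 mg/m2 on days 1-5, ATRA 45 mg/m2 daily on days 3-7, in 28-day cycles, 3 cycles (section 3.1).
- Reduced doses printed: 5-AZA 30 mg/m2 (Tables 6 and 7), ATRA 34 mg/m2 (Table 7 only).
- Section 8.1 reduction: 25% of the original dose per episode.
- Blood counts on treatment: Day 5 and Day 12, each +/- 3 days (Table 8 footnote), besides the 4-weekly visit.
- Marrow nadir days 10-17, recovery days 28-31 (section 5.1.6).
- Grade 3 neutropenia 5.9%, no grade 4 toxicity, in the cited phase II trial of 5-AZA at 40 mg/m2 on days 1-5 every 28 days (section 5.1.5).

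**Step 1: reproduce the printed doses.** 40 x (1 - 0.25) = 30 mg/m2, as in Tables 6 and 7. 45 x (1 - 0.25) = 33.75 mg/m2, which rounds to the 34 mg/m2 in Table 7.

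**Step 2: compare the rules for a first grade 3-4 hematologic event.**

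| | Section 6.2.1 / Table 6 | Section 8.1 |
|---|---|---|
| 5-AZA reduction | to 30 mg/m2 | 25%, to 30 mg/m2 |
| ATRA reduction | none stated | 25%, to 33.75 mg/m2, if both drugs are covered |
| What is held | the current dose, under a 5-AZA title | therapy, drug not named |

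The first 5-AZA step agrees. The ATRA reduction does not: the difference is 45 - 33.75 = 11.25 mg/m2 daily, or 25%. The hold is less clear-cut, because Table 6 also speaks of therapy in its long-interruption rule and neither place defines the word.

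**Step 3: does section 8.1 reach hematologic events?** Nothing in its wording excludes them. Table 6's recovery thresholds (ANC 1,000, platelets 50,000, hemoglobin 8) are the lower limits of its own grade 2 row, so they match the recovery level in section 8.1. The two rules can therefore apply to the same event.

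**Step 4: when it matters.** Both drugs are finished by day 7. A cytopenia found at the Day 12 count, or at nadir, bears mainly on the next cycle. Recovery can run to days 28-31, at or past the next cycle's first day. With 3 cycles, a cycle 1 event leaves two later cycles, a cycle 2 event leaves one, and a cycle 3 event leaves none. A hold within the ATRA course arises only for findings up to about day 7.

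**Step 5: how many patients.** 20 x 0.059 = 1.18, about 1 patient for neutropenia alone.

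**The case against.** The strongest reply is that no passage orders the two opposing things. A reader might infer that section 6 keeps ATRA at 45 mg/m2 through a hematologic hold while section 8.1 stops and cuts it. The documents do not support that as stated: continuation at full dose is inferred from Table 6's silence, and section 8.1 does not name ATRA in its hold and reduction sentences. This stands, and it limits the point to a conflict of scope.

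Section 8.1 could also be a loose restatement of section 6.2.2. It has the same sequence of grade 0-2, hold and 25% cut, and it speaks of symptoms where Table 6 uses counts. On that reading it would not touch hematologic events. The reading is possible, but section 8.1 does not say so and its wording is unrestricted. The contrast between the titles of Tables 6 and 7 also shows that section 6 covers both drugs only for non-hematologic events.

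A larger count is tempting. The package-insert list in section 5.1.6 gives 61% grade 3-4 neutropenia, which would mean 20 x 0.61 = 12.2 patients. That list is not tied to this trial's dose and schedule, whereas the 5.9% in section 5.1.5 comes from the same 5-AZA dose and schedule in prostate cancer, so the larger figure should not be used. Nor is neutropenia the commonest 5-AZA toxicity in either section: fatigue and constipation lead in 5.1.5 (41.2% each, against 17.6%), and thrombocytopenia ranks above it in 5.1.6.

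A reader might also infer that ATRA-only cycles would be counted toward the 8 weeks of treatment in sections 8.2 and 8.4. No passage provides for an ATRA-only cycle, and delaying both drugs is equally possible. Requiring both drugs in every counted cycle would be a new evaluability rule that ties replacement of patients more closely to toxicity.

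**Conclusion.** The point holds as a conflict of scope. After a first grade 3-4 hematologic event, section 6 states no change for ATRA, while section 8.1, read as covering the combination it discusses, calls for a hold and a 25% reduction. The documents do not say which applies. The conflict is firmer for the reduction than for the hold.

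The size is modest: a 25% difference in ATRA dose, in at most two later cycles, for about 1 of 20 patients with neutropenia and possibly more with other cytopenias. The count assumes that the rate seen with 5-AZA alone in castration-resistant disease carries over to the combination and this population. Section 5.1.5 gives both 26 and 36 as patient numbers for that trial, so the count is only an order of magnitude.

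A separate and more explicit contradiction lies between the same passages: Table 6 discontinues at the second occurrence, while section 8.1 allows two reductions and removes the patient at the third.

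**What to change.** Reconcile section 6.2.1/Table 6 with section 8.1 so that one passage states, for a grade 3-4 hematologic event, what happens to 5-AZA and what happens to ATRA, covering both the hold and the dose afterwards. Replace the free-standing rule in section 8.1 with a reference to that passage. Settle the second- versus third-occurrence conflict in the same edit. The investigator decides which rule governs; this review takes no view.

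The 8-week rule in sections 8.2 and 8.4 needs no change on this account. The cost is a wording amendment, with no new visits, data or sample size.

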### 6.2.2 Non-hematologic toxicities

5-AZA will be continued at the original dose if the adverse event is grade 0-2. For grade 3-4 toxicities related to study drug, 5-AZA will be held until improvement of symptoms to grade 2 or below. After the first episode, the dose will be reduced by 25%. After the second episode, the protocol therapy will be discontinued. The investigator will determine whether the toxicity is related to study drug. The investigator may prescribe any concomitant medications as necessary, except for other anti-cancer therapy, for the management of adverse effects.

ATRA will be continued at the original dose if the adverse event is grade 0-2. For grade 3-4 toxicities related to study drug, ATRA will be held until improvement of symptoms to grade 2 or below. After the first episode,

the dose will be reduced by 25%. After the second episode, the protocol therapy will be discontinued. The investigator will determine whether the toxicity is related to study drug. The investigator may prescribe any concomitant medications as necessary, except for other anti-cancer therapy, for the management of adverse effects.

**Table 7. Non-hematologic toxicity dose reductions for 5-AZA and ATRA**

NCI CTC Grade	5-AZA	ATRA
0-2	No change from original starting dose	No change from original starting dose
3 -4	Hold until resolved to $\leq$ Grade 2, then reduce to 30 mg/m^2	Hold until resolved to $\leq$ Grade 2, then reduce to 34 mg/m^2
Second episode of grade 3 or 4 toxicity	Remove subject from trial	Remove subject from trial

The administration of 5-AZA will be reported in a log book by the clinical trial staff. All patients will receive a study medication diary to log medication administration and adverse events for both 5-AZA and ATRA (See Appendix A).

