## 3. STUDY DESIGN

### **3.1 General Design**

This is a prospective, open-label, randomized, pilot study of reprogramming therapy in patients with recurrent PCa based on rising PSA only. Reprogramming therapy will include 5-azacitidine and all-trans retinoic acid. Expected duration of subject participation is 24 months.

All study will be assigned in a 1:1 randomization using computer random number generator to either the '5-AZA+ATRA' group or the 'no therapy' group. All enrollees will receive Leuprolide 7.5 mg x 1 on Day 1. On Day 29, they will initiate treatment phase 1. During this phase, patients in the '5-AZA + ATRA' group will receive treatment on a 28-day cycle, in the absence of prohibitive toxicities, for 3 cycles. During treatment phase 2, the 'no therapy' group will receive 5-AZA + ATRA on a 28-day cycle, in the absence of prohibitive toxicities, for 3 cycles. The treatment effect will be determined via comparing the intra-individual disease progression outcome at the end of the treatment phase 1, with period effect being separated through randomization. After treatment phase 1 and phase 2, all patients will be followed for a total of 24 months from the start of the study or until the events leading to discontinuation as outlined in Section 7.1 are observed. 5-AZA will be given subcutaneously on days 1-5 at a dose of 40 mg/m^2. ATRA, dosed at 45 mg/m^2 daily (divided into 2 doses), will be taken orally on days 3-7 of each cycle.

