## 7.1 Duration of Therapy

Treatment may continue for the 3-cycle treatment phase or until:

- Inter-current illness that prevents further administration of treatment
- Unacceptable adverse event(s) of the study regimen despite appropriate dose reduction and best supportive management
- Patient decides to withdraw from the study
- Noncompliance with study regimen or follow up appointments
- General or specific changes in the patient's condition render the patient unacceptable for further treatment in the judgment of the investigator.

The principal investigator will be notified and a case report form will be completed including the reason for study removal and the date the patient was removed. The patient should be followed up per protocol.

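### Table 7, section 8.1 and section 3.1 read as ending participation or follow-up after toxicity, while 6.2.2, 7.1 and the Follow Up Period text stop only the drugs: a minor but real inconsistency

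*Combined protocol and SAP*

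**What the plan says.** Some places end participation or follow-up:

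- Table 7, second non-hematologic grade 3-4 episode, in both drug columns: "Remove subject from trial".
- Section 8.1, which allows two dose reductions: "The third occurrence will result in removal of the patient from the study".
- Section 3.1 opens with "After treatment phase 1 and phase 2, all patients will be followed for a total of 24 months from the start of the study" but qualifies it with "or until the events leading to discontinuation as outlined in Section 7.1 are observed". The list in 7.1 includes "Unacceptable adverse event(s) of the study regimen despite appropriate dose reduction and best supportive management".

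Other places stop only the drugs, or continue follow-up:

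- Section 6.2.2, for the same episode as Table 7: "After the second episode, the protocol therapy will be discontinued".
- Table 6, second hematologic occurrence: "Discontinue protocol therapy".
- Section 7.1 presents its list as reasons to end treatment. It asks for a form giving the reason for, and date of, removal from the study, and then says "The patient should be followed up per protocol".
- Section 7, Follow Up Period, runs to 24 months from day 1 with two exceptions: radiographic progression and the start of another anticancer treatment.

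Table 8 sets assessments by calendar and ties only the extra blood counts to being on drug. The Treatment Phase(s) text in section 7 instead ties the restaging scans to every three cycles. That leaves the week-12 scan unclear for a patient who stops early.

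**The concern.** The question is what happens to the patient once the drugs are stopped, not which episode stops them. Table 7 and 6.2.2 give different actions for one and the same event, and staff may well consult the dosing table when toxicity occurs. Section 3.1 raises a separate problem: it makes 7.1 events an end to follow-up, which the Follow Up Period text does not.

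Several planned analyses need data after the drugs stop:

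- Section 8.4 keeps patients who stop for toxicity after 8 weeks in the efficacy analysis, so they need an end-of-phase outcome.
- PSA progression in 3.2.1 needs a confirmatory value at least 3 weeks later.
- The toxicity window in 6.2 extends up to 4 weeks beyond treatment.
- Section 2.2 compares time to progression over 24 months.

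In Phase 1 only the 5-AZA+ATRA arm receives the drugs, so any loss there would be one-sided and related to toxicity.

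**Working it through.** **1. The rules side by side**

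| Place | Trigger | Literal consequence |
|---|---|---|
| 6.2.2 | second related non-hematologic grade 3-4 episode | therapy stops |
| Table 7 | same episode | leaves the trial |
| Table 6 | second hematologic occurrence | therapy stops |
| 8.1 | third occurrence | leaves the study |
| 3.1 | any 7.1 event | 24-month follow-up ends |
| 7.1 | its listed events | treatment ends; patient is followed |
| Section 7, Follow Up Period | radiographic progression or other anticancer treatment | follow-up ends |

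Table 7 and 6.2.2 cannot both be followed literally. Nor can 3.1 and the Follow Up Period text.

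**2. How many patients.** The documents give no rate of repeat grade 3-4 events. Section 5.1.5 cites 4 of 36 patients stopping 5-AZA alone for toxicity: 4/36 = 11.1%, so 0.111 x 20 = 2.2 overall and 0.111 x 10 = 1.1 in the Phase 1 drug arm. This counts all toxicity stops, including those before 8 weeks, so it is only an upper guide. I assume 0-2 of 20.

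**3. Follow-up time at risk.** Inputs: Phase 1 starts on Day 29 (3.1), cycles last 28 days, a month is 30.44 days, and Phase 2 is assumed to follow Phase 1 directly.

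- Cycle 3 of Phase 1 runs from Day 85 (2.8 months) to Day 113 (3.7 months). Time lost: 24 - 2.8 = 21.2 to 24 - 3.7 = 20.3 months.
- Cycle 3 of Phase 2 runs from Day 169 to Day 197. Time lost: 18.4 to 17.5 months.

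In cycle 3 the last dose is on day 7 (Table 2). After that, stopping therapy changes no dosing in that phase, whereas literal removal still costs the end-of-phase outcome.

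**4. Effect on a Phase 1 rate.** At the planned 20% progression on drug, 10 patients give 8/10 = 80% progression-free. Losing one progression-free patient gives 7/9 = 77.8% (-2 points). Losing one who progressed gives 8/9 = 88.9% (+9 points).

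**5. Effect on power.** Section 8.2 states more than 80% power with 20 patients for 20% vs 60% progression at two-sided 10%. With discordant total s and difference d = 0.4, the McNemar formula is n = (1.645 √s + 0.842 √(s - d²))² / d².

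- Independent periods: s = 0.48 + 0.08 = 0.56, n = 19.4.
- Fully concordant periods: s = 0.40, n = 13.2.

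This agrees with the tabulated 14-19 to within rounding.

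The treatment test in 8.4 compares the within-patient difference D (period 1 minus period 2 progression) between arms by rank-sum. With drug first, P(D = -1, 0, +1) is 0.48, 0.44, 0.08 for independent periods and 0.40, 0.60, 0 for fully concordant ones. It is mirrored with drug second. Enumerating all outcomes with the tie-corrected normal test, PSADT strata ignored:

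| Patients per arm | Independent | Fully concordant |
|---|---|---|
| 10 + 10 | 83.1% | 99.6% |
| 9 + 10 | 81.9% | 99.5% |
| 8 + 10 | 78.8% | 98.1% |

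Type I error at 10 + 10 is about 9.7% to 10.0%.

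**The case against.** The strongest reply is that 7.1 largely settles the matter. In consecutive sentences it speaks of a patient removed from the study and then requires that patient to be followed. On that usage, removal means coming off treatment, and Table 7 is a dosing table written in the same loose vocabulary. This stands as evidence of intent. It does not cure 3.1, whose problem is not the word removal: it makes 7.1 events an end point for follow-up. The 3.1 clause does have a sensible meaning for other 7.1 items, such as withdrawal from the study.

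The 8.1 limb is weak, and that also stands. Under Tables 6 and 7 therapy has already stopped at the second occurrence, so removal at a third matters only if 8.1's episode count governs.

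The months in step 3 are calendar time, not endpoint information. If 60% of untreated patients progress within 12 weeks at a constant hazard (an assumption), median time to progression is 12 x ln 2 / (-ln 0.4) = about 9 weeks. Most of the lost months would then carry no first-progression data, although the progression date itself could still be lost.

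A reader might infer that the toxicity stopping rule or the safety set is compromised. The documents do not support this. The triggering event has already been counted, 8.4 keeps every patient with at least one dose in the safety set, and 8.2 counts replaced patients towards the stopping rule.

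**Conclusion.** The inconsistency is real and minor. The conflict between Table 7 and 6.2.2 is certain from the text, as is the conflict between 3.1 and the Follow Up Period text. Continued follow-up is probably what was meant.

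A reader might conclude that the plan intends to drop patients for toxicity, or that staff would certainly do so, and that the randomized comparison is therefore biased. That goes too far: 7.1 and the Follow Up Period text point the other way, and 8.4 presupposes outcomes for patients who stop after 8 weeks.

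Under literal application, perhaps 0-2 of 20 patients would be affected. They could lose the later course of the event, further adverse events in the 4-week window, and time-to-progression data. Those who stop after 8 weeks could also lose an end-of-phase outcome. Patients with under 8 weeks of treatment are replaced. One loss costs about 1 point of power with independent periods. The 79% case needs two losses in the same arm. The mixed model in 8.4 can still use a patient with one observed period.

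**What to change.** - In Table 7 and 8.1, replace removal with: *discontinue protocol therapy; continue study assessments and follow-up*.
- In 3.1, replace the reference to 7.1 events with the two stopping events in the Follow Up Period text, or withdrawal of consent.
- Add one sentence to section 7: after early stopping for toxicity, the PSA, adverse-event and week-12 imaging assessments in Table 8 continue by calendar.

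The rules on when therapy stops stay as they are. No separate schedule for patients with under 8 weeks of treatment is needed to cure this defect.

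The cost is a wording amendment plus visits and scans already planned, for about 0-2 patients. Measured against literal removal, it includes the 12-weekly follow-up visits: from Day 197 to month 24, (24 x 30.44 - 197) / 84 = about 6 per patient. It also includes any remaining 4-weekly visits and the week-12 scan of each phase still to run. Measured against the Follow Up Period text, those 12-weekly visits are already required.
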